
7) Setting of the Human Research

This research will be conducted at two comprehensive ophthalmology practices.

[name] - Levin and Luminais, PC in Thorndale, PA

[name] - Brandywine Eye Center in Wilmington, DE

8) Resources Available to Conduct the Human Research

Justify the feasibility of recruiting the required number of suitable subjects within the agreed recruitment period. For example, how many potential subjects do you have access to? What percentage of those potential subjects do you need to recruit?

We anticipate enrolling 3 subjects per month in the study.

Describe the time that you will devote to conducting and completing the trial within the agreed trial period.

How many potential subjects do you have access to? What percentage of those potential subjects do you need to recruit?

Describe the number and qualifications of your staff, their experience in conducting research, their knowledge of the local study sites, culture, and society.

The ophthalmologists who will be performing the SLT have years of experience performing SLT, and will continue to follow their patients after the procedure.

Describe your facilities.

Two comprehensive ophthalmology offices.

Describe the availability of medical or psychological resources that subjects might need as a result of anticipated consequences of the Human Research.

The patients will be monitored on a regular basis for adverse effects. The patients will receive appropriate follow up care and support.

Describe your process to ensure that all persons assisting with the trial are adequately informed about the protocol, the investigational product(s), and their trial-related duties and function.

All staff will be instructed on the study protocol, products, informed consent and protection of patient information.

9) Prior Approvals

None

10) Study Design

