a) Recruitment Methods

Potential subjects at the ophthalmology clinic will be approached by the investigator. The study will be explained and consent will be requested.

Describe the amount and timing of any payments to subjects.

Not applicable.

b) Inclusion and Exclusion Criteria

Inclusion criteria are patients who have been diagnosed with open-angle glaucoma, including ocular hypertension, pseudoexfoliation, and pigment dispersion syndrome. Patients must be greater than 18 years of age, with an initial IOP \geq 21mmHg,

Exclusion criteria include prior medical or laser therapy to lower IOP. Other exclusion criteria include previous incisional glaucoma surgery before the study period.

c) Local Number of Subjects

Indicate the total number of subjects to be accrued locally.

If applicable, distinguish between the number of subjects who are expected to be enrolled and screened, and the number of subjects needed to complete the research procedures (i.e., numbers of subjects excluding screen failures.)

Each of the three comprehensive ophthalmologists is anticipated to recruit 37 patients, for a total of 111 patients. This also accounts for the possibility that approximately 5% of patients enrolled will be lost to follow up.

d) Study-Wide Number of Subjects

If this is a multicenter study, indicate the total number of subjects to be accrued across all sites.

We plant to enroll a total of 111 patients.

e) Study Timelines

Describe:

- The duration of a subject's participation in the study.

One year

- The duration anticipated to enroll all study subjects.
- *Three years*
- The estimated date for the investigators to complete this study (complete primary analyses)
- *December 2017*

f) Study Endpoints

Describe the primary and secondary study endpoints. This is also called the primary outcome parameter. It is defined as the specific parameter or observation used to measure the effect of the intervention of interest. For example, a study may be conducted until the reoccurrence of disease, or change in blood pressure, or differences in proportions. Note that primary or secondary endpoints are not limited to clinical trials.

The primary endpoint is IOP at three months of follow up.

The secondary endpoint is 1 year of follow up or the point at which additional glaucoma therapy is required.

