Describe any primary or secondary safety endpoints. Examples may include evidence of liver toxicity, an inability to tolerate further chemotherapy, or other side effects.

. Anticipated AE include spike in IOP and iritis, which will be treated accordingly.

g) Procedures Involved in the Human Research

Describe and explain the study design.

We will be conducting a prospective evaluation of two treatment algorithms for SLT. The first algorithm will be a 180 degree treatment and the second algorithm a 360 degree treatment. Treatments will be done by Drs. [name], [name], and [name].

Patients will be pre-randomized to the 180 degree treatment or the 360 degree treatment by physician and by initial IOP (eg ≥ 21 mmHg up to 30mmHg and ≥ 30 mmHg).

Data that will be recorded for each patient include age, gender, race, glaucoma medications started during the study, the SLT protocol (number of spots, laser power setting and degrees of treatment). Baseline IOP before treatment will be recorded, in addition to measurement of IOP during a standardized follow up interval. Follow-up IOP measurements will also be recorded at one month, three months, six months and one year after laser. The physician will be masked as to the IOP result when measuring the IOP at each follow up visit Patients who require additional

glaucoma therapy will be censured from the study at that point. In addition, side effects and patient complaints will be noted.

For prospective studies:

Provide a description of all procedures being performed and when they are performed, including procedures being performed to monitor subjects for safety or minimize risks. Include procedures being performed already for diagnostic or treatment purposes and differentiate between these and the procedures performed solely for the research.

We will be performing SLT on the trabecular meshwork of eyes.

Describe procedures taken to lessen the probability or magnitude of risks.

Patients will be monitored after the procedure for symptoms or a spike in IOP

Identify which procedures are being done as part of the Human Research and which are being conducted anyway for other reasons (standard of care).

Describe all drugs and devices used in the research and the purpose of their use, and their regulatory approval status.

Describe the source records that will be used to collect data about subjects. Attach all surveys, scripts, and data collection forms.

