Describe the procedures to release data or specimens, including: the process to request a release, approvals required for release, who can obtain data or specimens, and the data to be provided with specimens.

i) Data Management

Describe the data analysis plan, including any statistical procedures.

Multiple IOP values will be analyzed over the one year follow-up period. In addition to degrees of SLT, other covariates will be used to adjust the observed effects. These covariates will include age, sex, and baseline IOP. A multiple variable linear model (analysis of covariance for repeated measures) will be used to evaluate the effectiveness of SLT over time. In addition, change in IOP from baseline values to last follow-up will be calculated and compared.

Provide a power analysis.

A review of previous retrospective studies, and prospective studies performed at glaucoma specialists' offices found: on average 360 degrees of SLT lowers IOP by 6.33 +/-5mmHg and 180 degrees of SLT lowers IOP by 3.86 +/-5mmHg. Based on these results and a 5% loss-of-follow-up rate, our power analysis shows that we will need 55 patients in each arm of the study.

Describe the steps that will be taken to secure the data (e.g., training, authorization of access, password protection, encryption, physical controls, Certificates of Confidentiality, and separation of identifiers and data) during storage, use, and transmission.

Patients will be assigned a number and that number will be entered in the database. No other patient identifying information will be entered in the database

Describe how data and specimens will be handled study-wide:

- What information will be included in that data or associated with the specimens?
- Where and how data or specimens will be stored?

The data will be stored on a Temple University password protected computer

- How long the data or specimens will be stored?
- *For the duration of the study*
-
- Who will have access to the data or specimens?

[name] and study investigators.

-
- Who is responsible for receipt or transmission of the data or specimens?

j) Provisions to Monitor the Data to Ensure the Safety of subjects

This section is required when Human Research involves more than minimal risk to subjects.

Describe the plans to periodically evaluate the data collected regarding harms and benefits to determine whether subjects remain safe.

The patients will be followed closely to monitor for harms and benefits

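### Physician is a randomisation factor but is not among the covariates named for the analysis model; naming it is a low-cost improvement

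*Combined protocol and SAP*

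**What the plan says.** Section 10(g), Procedures Involved in the Human Research, describes the allocation: "Patients will be pre-randomized to the 180 degree treatment or the 360 degree treatment by physician and by initial IOP". Section 10(c) gives the number of physicians: "Each of the three comprehensive ophthalmologists is anticipated to recruit 37 patients, for a total of 111 patients". They work in two practices (section 7).

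Section 10(i), Data Management, gives the analysis: "A multiple variable linear model (analysis of covariance for repeated measures) will be used to evaluate the effectiveness of SLT over time". Besides the extent of laser treatment, the adjustment is described as follows: "These covariates will include age, sex, and baseline IOP". Neither physician nor practice appears anywhere as a covariate, stratum or random effect.

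Two other statements bear on whether physician could matter. Section 8 says the treating ophthalmologists "will continue to follow their patients after the procedure". Section 10(g) says "The physician will be masked as to the IOP result when measuring the IOP at each follow up visit", so a physician takes the outcome measurement.

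**The concern.** A factor used to allocate patients should normally be named in the model that compares the arms. One of the two factors here is covered by baseline IOP; the other is not.

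Physician could plausibly predict follow-up IOP. The same ophthalmologists deliver the laser and follow their own patients, and the physician measures the follow-up pressure. A physician term would also absorb differences between the two practices.

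What is at stake is precision and calibration, not validity.

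- **Arms balanced within physician.** The treatment estimate is already about as precise as it can be. A model without physician leaves the between-physician variance in the residual, so the reported standard error is too large and the test rejects too rarely.
- **Arms not balanced within physician.** The test is correctly calibrated, but some real precision may be lost.

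**Working it through.** **Inputs from the documents.** Section 10(i) assumes "on average 360 degrees of SLT lowers IOP by 6.33 +/-5mmHg and 180 degrees of SLT lowers IOP by 3.86 +/-5mmHg", so the difference is 6.33 − 3.86 = 2.47 mmHg with SD 5. It allows for 5% loss to follow-up and asks for 55 per arm. Section 10(c) gives 3 × 37 = 111 patients, so about 111 × 0.95 = 105 are analysed. Alpha, sidedness, target power and between-physician variance are not stated.

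**The plan's own figure.** n per arm = 2 × SD² × (z_alpha + z_power)² / difference².

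- One-sided 5%, 80% power: 50 × (1.645 + 0.842)² / 2.47² = 50.7, so 51, and 51/0.95 gives 54. The t-test version gives 52, and 52/0.95 gives 55.
- Two-sided 5%, 70% power: also 51 then 54, or 52 then 55 by t-test.
- Two-sided 5%, 80% power: 65 then 69, or 66 then 70 by t-test, which does not reproduce 55.

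So 55 can be reproduced, but the documents do not show which alpha and power were used. Nothing below changes this number.

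**Assumed physician effect.** Let physician account for a share s of the residual variance of 25, with three equally spaced physician effects −a, 0, +a. Then 2a²/3 = 25s, and the highest-to-lowest gap is 2a = 10 × √(1.5s). Shares of 1%, 4% and 9% give gaps of 1.22, 2.45 and 3.67 mmHg. The 4% gap is about as large as the whole 2.47 mmHg treatment difference and the 9% gap exceeds it, so both are high-end cases.

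**Expected effect on the standard error.** With balance within physician, a model without physician should overstate the standard error by about 1/√(1 − s): 1.005, 1.021 and 1.048 at the three shares. The two-sided error rate is then about 2 × [1 − Φ(1.96/√(1 − s))], or 4.9%, 4.6% and 4.0%.

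**Simulation.** 40,000 trials per scenario, with 37 patients per physician, random 5% loss, total SD 5 taken as the residual SD after covariates, one visit and three other covariates. Each trial was analysed with and without two physician indicators. Allocation was split 18/19 within each physician, or 55/56 overall only. Changes were taken before rounding.

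| Physician share | Power without → with, balanced within physician | Change | Power without → with, balanced overall only | Change |
|---|---|---|---|---|
| 0% | 69.6 → 69.6 | 0.0 | 69.1 → 68.2 | −1.0 |
| 1% | 69.6 → 69.8 | +0.2 | 69.6 → 69.3 | −0.4 |
| 4% | 70.3 → 71.7 | +1.4 | 69.3 → 70.3 | +1.0 |
| 9% | 70.3 → 73.4 | +3.1 | 69.5 → 72.8 | +3.4 |

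The table is for a two-sided 5% test. With a one-sided 5% test, the changes are 0.0, +0.2, +0.8 and +2.2 points with balance within physician, and −0.6, −0.3, +0.8 and +2.5 points otherwise.

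**Type I error (two-sided).** Without physician it is 4.9%, 4.9%, 4.6% and 4.1% with balance within physician, close to the formula, and 5.0–5.1% with overall balance only. With physician it is 4.9–5.1% in every scenario.

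**Standard errors under the null.**

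- Balanced within physician, physician omitted: mean reported SE 0.986 against a true SD of 0.970 at 4%, and 0.987 against 0.950 at 9%.
- Balanced within physician, physician included, at 9%: 0.941 against 0.945. Only the reported SE changes materially.
- Balanced overall only, at 9%: the true SD is 0.990 without physician and 0.956 with it, so here real precision is lost.

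**Sensitivity.** A second simulation used permuted blocks of 4 within physician and IOP band, and adjusted for band only. At shares of 0%, 5% and 10%, two-sided power moved from 71.8 to 71.5, 72.5 to 74.0 and 72.0 to 75.5. Type I error without physician was 5.0%, 4.5% and 3.9%. The direction and size agree.

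**The case against.** The strongest reply is that nothing is invalid. The estimate is unbiased, any miscalibration is conservative, and the sample size does not rely on the adjustment. The covariate list is worded openly, so adding physician would not breach the plan. All of that stands, and it is why this is a suggestion rather than an error. An open list, however, leaves the choice until the data are in hand, and section 10(j) gives data review to the study investigators.

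The benefit also depends wholly on an unknown physician effect. The operators are experienced (section 8), section 21 promises efforts at standardisation across sites, and readings are masked. These general statements do not show a zero effect, but they give no support to large gaps. At a 1% share the gain is negligible, or slightly negative if balance is only overall.

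The overall-balance scenario fits the described design less well, since allocation is by physician. Block size is not stated, so imperfect balance within physician remains possible. That scenario is best read as a bound on the cost.

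Finally, the planned repeated-measures model was not simulated, SD 5 was taken as the residual SD, and 37 per physician is only anticipated. Absolute power levels depend on such choices (69.6% and 71.8% at zero physician effect in the two simulations), so the tenths should not be over-read.

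**Conclusion.** The point holds as a minor one. Patients are allocated by physician, and no section commits the analysis to adjusting for physician. There is no bias and no type I inflation. The benefit of naming physician ranges from none to about 3 points of two-sided power over assumed physician shares of 0% to 9%, with the error rate brought back to about 5% where the arms are balanced within physician. The worst case is a loss of about 1 point (69.1% to 68.2%), needing both no physician effect and balance only overall. These sizes rest on assumed physician variances, a single-visit model, residual SD 5 and a 5% test. Confidence in the size is medium; the textual mismatch is clear.

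**What to change.** In section 10(i), replace the covariate sentence with one such as: *The model will adjust for physician (three levels), baseline IOP (continuous), age and sex.* If the separate comparison of change to last follow-up is also made with a model, use the same physician term there.

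Carry the physician used for allocation into the analysis dataset as a coded field. The data items listed in section 10(g) do not include it, and the adjustment cannot be made later if it is not kept.

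The cost is two degrees of freedom, one data field and no extra patients. If the arms are balanced within physician, the power cost is nil.
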